8.7 Scientific Committee Review

A Scientific Committee (SC) has been appointed for this study. Initially, the committee consists of the investigators, the study Medical Monitor and two physicians specialized in osimertinib (AZD9291) therapy.

The SC will meet on demand to review, discuss and evaluate all of the collected safety data. In the event of a safety issue, a meeting can also be called at any time at the request of an investigator participating in the study. At these meetings, MedSIR and the participating investigators must reach a consensus on safety data. MedSIR will prepare minutes for these meetings and submit them to each investigator for comment prior to finalization.

The study site Investigators and MedSIR will review patient data at least every four months. Each study site investigator will regularly review patient data to detect serious side effects.

8 ETHICAL CONSIDERATIONS

9.1 Regulatory and ethical compliance

The study will be conducted and reported in accordance with the protocol, the International Conference on Harmonization (ICH) Guidelines, and the ethical principles laid down in the Declaration of Helsinki. The study will also comply with European Regulation No. 536/2014 and any applicable local regulations.

9.2 Ethics Committee:

The conduct of the study must be authorized by a duly constituted EC. Authorization is required for study protocol, protocol amendments, informed consent forms, patient information sheets and promotional materials.

Wherever necessary, the investigator and/or sponsor should contact the EC to ensure that accurate and timely information is being provided at every phase of the study.

The principal investigator and/or sponsor are responsible for providing, when required, written summaries of the study status to the EC annually or more frequently, in accordance with the requirements, policies and procedures set out by the EC.

2. LIST OF ABBREVIATIONS AND DEFINITION OF TERMS

95%CI	95% confidence interval
AE	Adverse Event
ALT	Alanine transferase
ANC	Absolute neutrophil count
AST	Aspartate aminotransferase
BOR	Best overall response
cORR	Confirmed overall response rate
CNS	Central nervous system
CR	Complete response
CRF	Case Report Form
CTCAE	Common terminology criteria for adverse events
DCR	Disease control rate
DoR	Duration of response
ICH	International conference of harmonisation
ECG	Electrocardiography
ECOG	Eastern cooperative oncology group
EGFR	Epidermal growth factor receptor
EORTC	European organisation for research and treatment of cancer
HIV	Human immunodeficiency virus
IC	Informed consent
IMP	Investigational Medical Product
ILD	Interstitial Lung Disease
LNL	Lower normal limit
MRI	Magnetic resonance imaging
mRNA	Messenger ribonucleic acid
N	Number of patients
NA	Not applicable
NCI	National Cancer Institute
NSCLC	Non-Small Cell Lung Cancer
OR	Overall response
ORR	Overall response rate
OS	Overall survival
PD	Progressive disease
PFS	Progression-free survival
PET-CT	Positron emission tomography/computed tomography
PMF	Probability of mass function
PR	Partial response
RECIST	Response evaluation criteria in solid tumours
SAP	Statistical Analysis Plan
SC	Steering committee
SD	Stable disease
TTF	Time to failure
TS	Tumor Shrinkage
UMVUE	Uniformly minimum variance unbiased estimator
UNL	Upper normal limit
US	United states

4. INTRODUCTION

4.1 Preface

We can state that in EGFR-mutation-positive NSCLC, in addition to the molecular diagnosis, it is necessary to quickly validate and implement a kit as part of clinical practice for the detection of a predictive biomarker panel that will allow for adequately personalized treatments using EGFR TKIs in monotherapy. To this end, we propose to begin a phase IIa clinical trial of osimertinib (AZD9291) in patients with a recent diagnosis of NSCLC with EGFR mutations and with the concomitant pre-treatment T790M mutation. The mutation will be detected in tumor tissue using a highly sensitive assay for T790M, based on laser microdissection and a peptide-nucleic acid clamping PCR.

4.2 Purpose of the analyses

These analyses will assess the efficacy and safety of osimertinib (AZD9291) in patients with advanced non-squamous NSCLC with EGFR mutations and the EGFR T790M mutation at diagnosis.

5. STUDY OBJECTIVES AND ENDPOINTS

5.1 Study objectives

To evaluate the efficacy of osimertinib (AZD9291), in terms of the objective response rate (ORR) in patients with advanced non-squamous NSCLC with EGFR mutations and the EGFR T790M mutation at diagnosis, as defined by RECIST 1.1 criteria.

5.2 Endpoints

(ICH E9; 2.2.2)

The efficacy study endpoints will be derived in accordance with Per Response Evaluation Criteria in Solid Tumours (RECIST v1.1) assessed by magnetic resonance imaging (MRI) or computed tomography scan (CT). The next endpoints have been defined:

Complete Response (CR): Disappearance of all target and non-target lesions and no new lesions.
Partial Response (PR): $\geq 30\%$ decrease in the sum of diameters of Target Lesions (TL) (compared to baseline) and no new lesions.

Stable disease (SD): Neither sufficient shrinkage to qualify as a response nor sufficient growth to qualify as progression.

Progressive Disease (PD): $\geq 20\%$ increase in the sum of diameters of TLs and an absolute increase in sum of diameters of $\geq 5\text{mm}$ (compared to the previous minimum sum) or progression of NTLs or a new lesion.

Not evaluable (NE): TL response is missing and there is no evidence of progression of NTLs and no new lesions.

BOR is the best response (by investigator assessment) a patient has achieved where the order of best to worst is CR, PR, SD, PD, NE prior to or at progression and prior to further anti-cancer therapy.

Additionally censoring strategies in time to event outcomes will be defined in accordance with Guidance for Industry Clinical Trial Endpoints for the Approval of Cancer Drugs and Biologics from food and drug administration.

5.2.1 Primary endpoint

Confirmed objective response rate (cORR) is defined as the number of patients with complete response (CR) and partial response (PR), confirmed at least 4-6 weeks after the initial response, divided by the number of patients in the analysis set. Tumor response will be defined as best response, based on local investigator's assessment according to RECIST criteria guidelines (version 1.1).

5.2.2 Secondary endpoints

The following exploratory endpoints will be analysed:

- Objective response rate (ORR) is defined as the number of patients with complete response (CR) and partial response (PR) divided by the number of patients in the analysis set. Tumor response will be defined as best response, based on local investigator's assessment according to RECIST criteria guidelines (version 1.1).
- Disease control rate (DCR) is defined as the patients with CR, PR, or SD relative to all participants in analysis set. Participants who do not have on-study radiographic tumor reevaluation, who received anti-tumor treatment, who died, progressed, or dropped out for any reason prior to achieving reaching a CR or PR and a best response of SD was counted as non-responders in DCR.
- The progression-free survival (PFS) as assessed by investigator is defined as the time from the date of randomization to the date of the first documentation of objective tumor progression as per RECIST v1.1 or death due to any cause in the absence of documented PD, whichever occurs first. If tumor progression data include more than 1 date, the first date will be used. PFS (in months) will be calculated as (first event date – randomization date +1)/30.4. Progression is defined using RECIST v1.1, as a 20% increase in the sum of diameters of target measurable lesions above the smallest sum observed (over baseline if no decrease in the sum is observed during therapy), with a minimum absolute increase of 5 mm, or unequivocal progression of pre-existing non-target lesions, or the appearance of new lesions.
- Overall survival (OS) is defined as the time from treatment start to the time of death due to any cause.
- Time to treatment failure (TTF) is defined as the time from treatment start to the time at which the patient discontinues treatment due to any cause, including disease progression assessed by the investigator as per RECIST v1.1, toxicity, death or at the patient's request.
- Duration of response (DOR): is defined as the time from the date of first documented response (CR or PR that was subsequently confirmed) until the date of documented progression (PD) or death in the absence of disease progression (by investigator assessment).
- Tumor shrinkage (TS) is defined as the percentage of tumor shrinkage from baseline (obtained from the sum of the largest diameters of the target lesions) per RECIST v1.1 criteria.

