 Disease control rate (DCR) is defined as the percentage of patients with CR, PR or stable disease for a minimum of 24 weeks, assessed in accordance with the modified Response Evaluation Criteria in Solid Tumors (RECIST v. 1.1), version 1.1.

 Tumor shrinkage (TS) is defined as the percentage of tumor shrinkage from baseline (obtained from the sum of the largest diameters of the target lesions) according to RECIST v1.1 criteria.

Molecular secondary endpoints

- Correlation ratio of mutational status and documented clinical response.
- A progress curve showing the EGFR mutational status (including the T790M mutation) in plasma and serum longitudinally.
- Percentage levels of BIM mRNA as well as mRNA levels of other biomarkers related to EGFR TKI response.
- Percentage of patients with mutations at the site of covalent binding to the drug (C797) or other mutations in tissue and correlation ratio of documented clinical response.

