Physical examination: A complete physical examination should include an examination of head, eyes, ears, nose, and throat as well as cardiovascular, dermatological, musculoskeletal, respiratory, digestive, genitourinary and neurological systems. Changes to abnormalities identified during the baseline period should be recorded at all subsequent physical exams. New or worsening abnormalities should be recorded as adverse events, if applicable.

Protocol date: May 21, 2018

Version 3

Physical exams should also include, as part of tumor assessment, evaluation of presence and degree of increase of lymph nodes, hepatomegaly and splenomegaly. Limited physical exams will focus on symptoms.

Response and tumor assessments: Tumor response will be assessed for all patients, unless they withdraw from the study for any reason not attributable to disease progression confirmed radiologically or clinically and who have not received an acceptable complete assessment of the disease. The measurable and non-measurable disease should be documented at screening and be re-assessed at every tumor assessment thereafter. The initial assessment of tumor response will be performed at the end of cycle 4. Thereafter, an efficacy follow-up will be carried out for all patients every 12 weeks during the study period, until disease progression, death, treatment discontinuation or study completion. In this study, response and disease progression will be assessed using the Response Evaluation Criteria in Solid Tumors (RECIST criteria) (version 1.1) (Appendix 2: Response Evaluation Criteria in Solid Tumors Guidelines (RECIST criteria) (version 1.1)).

A PET-CT, CT or MRI of at least the chest and abdomen should be performed at screening. If a positron emission tomography (PET)/CT is used in tumor assessments, the CT portion of the PET/CT should meet diagnostic quality requirements. Tumor assessments should include an assessment of all known and/or suspected sites of the disease wherever possible. Patients should have a series of selected lesions that can be assessed at each tumor assessment.

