6.2 Visits schedule

(ICH E3; 9.5.1. ICH E9; 2.2.2)

The following table presents the relation between visits and medical assessments planned for this study:

SAP Table. 1 Visits schedule

Assessment	Screening	Baseline	Treatment period: 2 -weeks post-baseline evaluation	Treatment period: Complete evaluations	Treatment period: Routine evaluations	End of treatment visit: After progression or at the end of treatment for any other reason	Follow-up
	(2-4 weeks as maximum before baseline)	Day 0 (pre-treatment)	After 2 weeks	After 12, 24, 36, 48, 60, 72 weeks from first dose	After 6, 18, 30, 42, 54, 66, 78 weeks from first dose	Within 4 weeks after end of treatment (only if end of treatment is not confirmed in some of the scheduled full visits)	After progression or end of treatment for any other reason, after 12,24,36,48, 60, 72, 78 weeks after first dose
Written Informed Consent	X						
Sample (tissue) to the central lab	X [1]					X (if available)	
Medical History		X		X			
Physical examination, ECOG Performance Status, Vital Signs, body weight		X [2]		X [2]	X [2]	X [2]	
Recording of symptoms		X		X	X	X	
Pregnancy Test		X [3]					
Hematology		X [4]		X [4]	X [4]	X [4]	
Renal function		X [4]		X [4]	X [4]	X [4]	
Blood Chemistry		X [4]		X [4]	X [4]	X [4]	
Coagulation		X [4]		X [4]	X [4]	X [4]	
Urine dipstick test for analysis of proteinuria		X [4]		X [4]	X [4]	X [4]	
ECG		X [5]		X	X (only if clinically required)	X	
Tumor Assessment		X [6]		X [6]		X [6]	

Serum/plasma sample for translational research		X	X	X		X	
Antineoplastic therapy		X	X	X	X	X	X
Concomitant Medication	X		X [7]	X [7]	X [7]	X [7]	
Adverse Events			X	X	X	X	X [8]
Survival			X	X	X	X	X

1. EGFR results from test performed locally in the same laboratory than the central one up to 28 days before inclusion will be accepted.
2. Vital signs include pulse and temperature.
3. A negative serum or urine pregnancy test up to 7 days before inclusion will be accepted.
4. Hematology, renal function, blood chemistry and coagulation tests performed up to 72 hours before inclusion and before the corresponding date of each visit will be accepted.
5. ECG performed up to 14 days before inclusion and before the corresponding date of each visit will be accepted.

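### The SAP drops the protocol's 24-week minimum for stable disease from the disease control rate, so one stable scan at week 12 counts as disease control and the reported rate is inflated.

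*SAP*

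**What the plan says.** Protocol section 2.2 states that DCR "is defined as the percentage of patients with CR, PR or stable disease for a minimum of 24 weeks", assessed by RECIST 1.1.

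SAP section 5.2.2 keeps the name and drops the duration: "Disease control rate (DCR) is defined as the patients with CR, PR, or SD relative to all participants in analysis set". The next SAP sentence lists patients to be treated as failures. It ends with those who "dropped out for any reason prior to achieving reaching a CR or PR and a best response of SD was counted as non-responders in DCR". It contains no duration, and its grammar is broken.

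The SAP's supporting definitions in section 5.2 do not bring the 24 weeks back. SD is "Neither sufficient shrinkage to qualify as a response nor sufficient growth to qualify as progression", with no minimum time from the start of treatment. For best overall response, "the order of best to worst is CR, PR, SD, PD, NE prior to or at progression and prior to further anti-cancer therapy". Sections 7.2 (secondary analysis), 7.5 (subgroups) and 7.6 (missing data) use DCR without a time minimum. Section 9, which summarises changes to the protocol, mentions only the interim review and the closure of accrual.

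On timing, protocol section 5.2 says "The initial assessment of tumor response will be performed at the end of cycle 4". The SAP visit table (section 6.2) places the complete evaluations, which include the tumor assessment, "After 12, 24, 36, 48, 60, 72 weeks from first dose".

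**The concern.** The two documents define different endpoints under one name. The SAP version is the looser, and the change is not declared. If the analysis follows the SAP, as one would expect, the trial will report as its protocol DCR a rate that includes patients the protocol counts as failures.

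The difference matters in this trial because of the sparse imaging. With scans 12 weeks apart, a single stable scan is enough for SD as best response, and the 24-week requirement is what makes the patient pass a second scan. The looser rate would appear in two places: the DCR estimate with its 95% confidence interval (SAP 7.2) and the comparison of DCR between EGFR mutation types (SAP 7.5).

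**Working it through.** **Figures in the plan.** The documents give no expected or target DCR, so there is no DCR figure to reproduce. The ORR design (21 then 73 patients, stop at 11 or fewer, success at 45 or more) does reproduce. Summing Bin(x; 21, p) × P(X ≥ 45 − x | 52, p) over x = 12 to 21 gives 0.0249 at p = 0.50 and 0.9004 at p = 0.70, against the stated 0.025 and 90%. DCR does not enter this calculation.

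**Classification.** Cycle 4 ends at 4 × 21 days = 84 days = 12 weeks, and the next scan is at week 24.

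| Patient | SAP best response | DCR under SAP | DCR under protocol |
|---|---|---|---|
| SD at week 12, progression at week 24 | SD | success | failure |
| SD at week 12, no later scan | SD | success | 24 weeks not shown; missing counts as failure (protocol 8.5) |
| SD at weeks 12 and 24 | SD | success | success |
| Progression at week 12 | PD | failure | failure |

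No row moves the other way. Hence

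SAP DCR − protocol DCR = P(best response SD) × P(SD does not last 24 weeks | best response SD) ≥ 0,

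which is zero only if every SD lasts 24 weeks. The protocol wording could also be read as applying the 24 weeks to CR and PR. On that reading the SAP is still the looser definition.

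**Size.** Both factors are assumptions, because the documents give neither. Take SD as best response in 20-25% of patients and exponential time to progression among them. For those stable at week 12,

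P(progress by week 24) = 1 − exp(−ln 2 × 12 weeks / median).

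Months are converted at 30.4 days, as in SAP 5.2.2. Products use unrounded probabilities.

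| Median | Weeks | Probability | Excess, SD share 20% | Excess, SD share 25% |
|---|---|---|---|---|
| 3 months | 13.0 | 0.47 | 9.4 points | 11.8 points |
| 6 months | 26.1 | 0.27 | 5.5 points | 6.8 points |
| 9 months | 39.1 | 0.19 | 3.8 points | 4.8 points |
| 12 months | 52.1 | 0.15 | 3.0 points | 3.7 points |

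The range is about 3 to 12 percentage points. A wider grid, with an SD share of 10-30% and 25-75% of SD not reaching 24 weeks, runs from 0.10 × 0.25 = 2.5 points to 0.30 × 0.75 = 22.5 points.

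**Worked example** (assumed: ORR 70%, SD 20%, half of SD shorter than 24 weeks; Clopper-Pearson intervals). The nominal rates are 70 + 20 = 90% under the SAP and 70 + 10 = 80% under the protocol. Rounded to whole patients:

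- 73 patients: 66/73 (95% CI 81.2-96.1%) under the SAP, 58/73 (68.4-88.0%) under the protocol.
- 21 patients: 19/21 (69.6-98.8%) under the SAP, 17/21 (58.1-94.6%) under the protocol.

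Each reclassified patient moves DCR by 1/73 = 1.4 points or 1/21 = 4.8 points. SAP section 9 says accrual closed after the interim review, but the final number of patients is not stated.

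**Is there a data reason for the change?** None is visible. The interim window is 42 weeks and follow-up runs to 78 weeks, so the week-24 scan lies inside both.

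**The case against.** The best counter-argument rests on the SAP's non-responder sentence. It can be read to mean that patients who progress or drop out without CR or PR, having SD as best response, are failures. The patient stable at week 12 and progressing at week 24 would then fail under the SAP too. A patient stable to week 36 who then progressed would also fail, which is stricter than the protocol. This reading is strained. It contradicts the sentence before it, which counts SD as disease control, and it contains no 24-week rule. The natural reading is that patients who fail before reaching CR, PR or SD are non-responders, and then week-12 SD still counts. What stands is that the sentence is ambiguous and must be rewritten.

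The size also rests wholly on assumptions. The calculation supports the direction better than the magnitude. If the final number is near 21, an excess of 3 to 12 points is only about 0.6 to 2.5 patients, well inside confidence intervals that span roughly 29 to 37 points.

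Finally, the consequences are limited. DCR has no hypothesis, target or alpha, and SAP 7.8 treats secondary analyses as supportive. Subgroup comparisons are exploratory with q-value adjustment. Progression-free survival and the counts of CR, PR, SD and progression are also reported, so early progression would not be hidden. This limits the importance of the point but does not justify using one name for two endpoints.

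**Conclusion.** The concern holds. The SAP's DCR omits the protocol's 24-week minimum for SD, nothing else in the SAP restores it, and the change is not recorded. On the plain reading of SAP 5.2.2 any resulting error is upward. The excess is about 3 to 12 percentage points if 20-25% of patients have SD as best response and their median time to progression is 3 to 12 months (exponential). Wider assumptions give 2.5 to 22.5 points. The confirmed-response analysis, the 11-of-21 futility rule and the 45-of-73 success rule are unaffected. This should be corrected, but it does not threaten the trial's main conclusion.

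**What to change.** In SAP 5.2.2, define disease control as CR, PR, or SD lasting at least 24 weeks from first dose, meaning no progression up to and including the week-24 scan within its window. The protocol gives no starting point for the 24 weeks, so first dose is a choice to be stated as such.

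Two details belong in the same edit:

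- Rewrite the non-responder sentence so that it has one meaning and agrees with the restored definition. A patient with SD but no evaluable scan at or after the week-24 window should count as a failure, in line with the existing missing-data rule.
- State which window applies to the week-24 scan. Protocol section 5.2 allows ±3 working days, while SAP section 6.2 accepts PET-CT or MRI up to 14 days before a visit. Without a rule, a scan just before day 168 (24 × 7) would fail a strict 24-week criterion.

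If the any-duration rate is wanted, report it separately as best response of CR, PR or SD. If the sponsor prefers that version as the DCR itself, record and justify the change in SAP section 9 and report both.

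The cost is one SAP paragraph and one derivation. The scans are already scheduled, so there is no added burden on patients. The DCR figure will be equal or less favourable.

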5.2.3 Exploratory endpoints

The following exploratory endpoints will be analyzed:

- Correlation ratio of mutational status and documented clinical response.

- A progress curve showing the EGFR mutational status (including the T790M mutation) in plasma and serum longitudinally.
- Percentage levels of BIM mRNA as well as mRNA levels of other biomarkers related to EGFR TKI response.
- Percentage of patients with mutations at the site of covalent binding to the drug (C797) or other mutations in tissue and correlation ratio of documented clinical response.

5.2.4 Safety endpoints

The following safety endpoints will be analyzed:

Patient safety and adverse events will be assessed using the Common Terminology Criteria for Adverse Events (CTCAE) of the U.S. National Cancer Institute (NCI), version 4. Grade 3 or 4 adverse events and serious adverse events will be assessed to determine the safety and tolerability of the various combinations of drugs.

6. STUDY DESIGN

6.1 General study design and plan

(ICH E3;9.)

Identify the study design, including the following:

- This is a multicenter, open-label, single-arm non-controlled phase IIa trial. The design of this study is divided into three well-defined phases:
 - **Screening phase**

During this phase, subject eligibility is determined, including the genotyping of the tumor and documentation of baseline characteristics.

[figure not shown]
- **Treatment phase:**

When a patient carrying both mutations is identified and the study screening criteria have been met, the patient will receive a dose of osimertinib (AZD9291) 80 mg every 24 hours, in tablets for oral administration. The study treatment will continue until one of the following situations arises:

- Disease progression is confirmed radiologically and unequivocally, except for new metastases in CNS or isolated progression of previously-treated lesions in the CNS.
- Adverse event(s) which, according to the protocol or in the opinion of the investigator, can cause serious or permanent damage or which rule out further treatment with the study drug.
- General or specific changes in the patient's health state which, in the opinion of the investigator make further treatment unacceptable.
- Major study protocol non-compliance.
- Patient's withdrawal from the study.
- Dead.
- After a maximum of 78 weeks from the patient first study treatment dose intake.
- Study is canceled by the Sponsor.

- **Follow-up phase:**

Once the treatment phase is completed, a biopsy should be performed to identify acquired mechanisms of resistance to the drug and the follow-up phase will begin.

